4.2 Inclusion of Vulnerable Subjects and Special Populations

Phase One: This study will include VHA medical and mental-health care providers who may feel pressured or also be vulnerable to coercion or undue influence to participate in research. Special considerations have been taken to protect this group and these employees, by ensuring that their supervisors will not be informed of their participation by study staff, as well as assurances that their participation will be kept confidential and all data collected will be anonymized and deidentified.

Phase Two and Phase 3: Vulnerable participants include those with chronic pain disorders, as these individuals can often have comorbid mental health concerns. Another population to be included is that of the Veterans themselves. They are accustomed to taking and following direct orders, thus introducing a further need for researchers to prevent coercion either directly or indirectly. Veterans will be given ample time to read and consider informed consent, with other treatment options presented by investigators. Family members, significant others, and primary treatment teams may also be involved in the decision-making process if the Veteran wishes. They are also informed that refusal to participate will be accepted without hesitation at any time and will not change their eligibility for VA services, treatment, disability payments, or other related VA benefits. Research staff will evaluate each subject at the end of the phone screen and/or usability testing session to ensure that they have not experienced significant distress or exacerbation of their symptoms as a result of their participant. The evaluation will consist of asking the subject about (1) feelings of distress and (2) desire for additional support because of distress. Anyone experiencing distress and desiring support will be provided with informal support, and if necessary taken to formal providers

4.3 Inclusion of Incompetent Subjects

Not applicable.

4.4 Inclusion/Exclusion Criteria

Phase One:

Inclusion Criteria

- 1) Currently working at the VA Bedford Healthcare System or one of its affiliated CBOCs in a clinical capacity, including mental health, physicians, nursing, pharmacists, or primary care/behavioral health staff
- 2) Currently seeing Veterans to assist in their management of chronic pain

Exclusion Criteria.

- 1) Any cognitive or physical impairment that would interfere with study participation of using a computer and providing verbal feedback.

Phase Two:

Inclusion Criteria

- 1) Current diagnosis of non-cancer chronic pain
- 2) Competent to provide written informed consent
- 3) Ages 18 and older
- 4) Access to the internet at least weekly through a computer

Exclusion Criteria

- 1) Any cognitive or physical impairment (e.g., auditory or sight issues issues) that would interfere with study participation of using a tablet/computer and providing feedback.

Phase Three:

Inclusion Criteria

- 1) Current diagnosis of non-cancer chronic pain, defined as 1) at least one pain-related diagnosis indicated by an ICD-9 or -10 code related to either Musculoskeletal pain or Joint Problems/Osteoarthritis or 2) presence of chronic pain of at least mild to moderate severity as indicated by two or more NRS pain scores of ≥ 4 at three separate VA outpatient visits in past year based on a CPRS record review;
- 2) Has a working, high-speed wireless internet connection at home, or is willing to access sessions either at the Bedford VAMC by using a provided laptop in a secure space
- 3) Competent to provide written informed consent
- 4) Ages 18 and older.

Exclusion Criteria

- 1) Any current or lifetime DSM-5 psychotic disorder
- 2) Current or recent (within 1 month of study entry) DSM-5 alcohol or drug use disorder
- 3) Current use of any other chronic pain-related behavioral or psychological treatment
- 4) Any cognitive impairment that would interfere with study participation
- 5) Clinically significant suicidality within the past year
- 6) Presence of any clinical features requiring a higher level of care (inpatient or partial hospital treatment)
- 7) Any cognitive or physical impairment that would interfere with study participation of using a laptop/computer and providing feedback]

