Individual feedback sessions at the end of the full study will be analyzed together to gather information for refining the treatment to make it acceptable to patients. After receiving the totality of information from 10-12, the researchers will amend the program with a potential solutions i.e, adding VA-specific pain information, text size or text color being altered. Some platform usability and intervention-specific challenges will be addressed with introductory handouts/tutorial materials/orientation to the program at the beginning of the intervention session.

Phase 2: Data Collection:

Qualitative Combined Usability and Contextual Interview. We will focus on usability and feasibility for Phase 2. During the 2 hour at-home usability sessions, participants will assess the usability of the VACT-CP intervention using a “think-aloud protocol”, verbalizing their thoughts as they navigate the website and Coach Anne. After a period of exploration with the site, the research staff will use a pre-created protocol to ask Veterans to interact with Coach Anne through one of the VACT-CP modules (i.e., responding to her queries, entering therapy goals, completing in-session assessments, interacting with the virtual therapist generally). As the participant navigates the intervention website on their computer, their actions will be recorded through a screen-share recording electronically, and the Veterans comments will be recorded via the audio. [name] will observe the actions in real-time during the session via the same technology platform.

Usability Assessment Procedures

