Eligible Veterans will first complete baseline demographic and health measures provided over the phone (approximately 30 mins). Following the baseline assessment, Veterans will be provided with a quick overview of the site and interaction system to help Veterans access and understand different portions of the user interface and treatment set-up, during which time they will be asked questions and recorded as a usability interview. Next, Veterans will be provided with verbal instructions for use, and begin their walk- through of a portion of the treatment (approximately 10 mins). During this time, the Veterans will take part in a contextual interview wherein Veterans move through the system unguided and are observed and asked questions about their experience (approximately 30 minutes). After this, additional, usability items (25 mins) and open-ended questions will be asked regarding Veteran preferences (approximately 20 minutes).

For purposes of feedback and iterative program development, the Veteran will only be provided a portion of the VACT-CP program during this time, during which time their use of the system will be recorded. Approximately 4-5 Veterans will be recruited and participate in this usability testing at a time, with 3 different usability testing arms, in order to allow for time to iteratively address any functionality issues or concerns with the user interface. Following this walkthrough, participants will be provided with measures of demographics, usability and health information technology use, including a retrospectively worded version of the Usability Survey items (e.g., I enjoyed using the VACT-CP program) and a semi-structured qualitative exit interview. Participants will receive a \$40 gift card for their virtual research session, which should take approximately 2 hours.

Assessment Measures At Beginning of Session

A broad range of reliable and valid measures will be used to provide an assessment of chronic pain difficulties, demographic information, and technology use, technology interest, and comfort.

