Qualitative Combined Usability and Contextual Interview: Veterans will be observed while interfacing with the VACT-CP system, recorded, and asked questions by the interviewer. This will consist of specific questions related to the different parts of the system the veteran interacts with (e.g., the virtual coach design, structure of the modules, feedback system) as well as more open-ended questions when not provided with specific cues (e.g., what are you trying to get to from this page, what could be better about how this is set-up, etc.). Questions will be open-ended in nature, and address the extent of any problems with accessing and using the VACT-CP treatment online, how they might perceive the usefulness or importance of VACT-CP focal areas of treatment, whether they would recommend this treatment to a fellow Veteran, and any problems or concerns they may have with using the VACT-CP program.

Using this additional, open-ended interview protocol, we will also inquire as to whether they would be interested in using the VACT-CP treatment at home beyond this session, and the role of their virtual coach in the patient's interest in the treatment, and about past strategies or tools the patient used to address their chronic pain or tools the patient used to address their chronic pain issues and whether the VACT-CP treatment might seem more useful than prior options or strategies. Finally, participants will be asked to indicate what, if any, changes they would make to the treatment to assist in self-management of their chronic pain. This will also include assessing their interests in complementary and alternative methods of pain management (stretching, yoga, progressive muscle relaxation, etc.) to assess if it would be useful and feasible to add these options to the platform later if desired. The interview will be video-recorded and coded to look for similar themes, difficulties, revisions, and strengths of the system.

Intervention Revision

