We will focus on usability of the VACT-CP system in home setting to test Aim 3a. Usability will be primarily measured via the Usability Survey Subscales for antecedent user features (e.g., health care need). The Usability Survey Subscales and System Usability survey will assess for acceptability features at both pre- and post-intervention (e.g., perceived ease of use, perceived usefulness, intrinsic motivation, and system usability) We will then assess if these usability factors relate to intended and actual use statistically using bivariate correlations.

To address Aim 3a, we will first compile descriptive statistics for each of the ITAM measures, determine Cronbach's alphas for each of the ITAM component subscales, and compute bivariate Pearson's correlations to assess relationships between acceptability, antecedent and intention and actual use factors of the ITAM. Next, where we have sufficient data from participants receiving the same intervention we will use multiple linear regression models for VACT-CP use to model which acceptability features (intrinsic motivation, perceived ease of use, perceived usefulness, system usability) are most strongly related to behavioral intention to use modules and with actual use.

Additional data will be provided by the semi-structured qualitative interviews and tracking of any calls to research staff with concerns. Analysis of post-intervention interviews will be done using notes taken by one of the team members during the exit interview; interviews will also be audiotaped for later use if needed. [name] and research staff will apply CRQ qualitative analytic techniques (see Phase 2 Data Analysis plan) to these data (e.g., coding for and extracting major themes) to assess both barriers and facilitators to use of the VACT-CP system, and individual demographic user factors that impact use. Finally, we will behaviorally assess feasibility by measuring the proportion of individuals who successfully complete the 8 week trial with at least 5 completed modules, which would be 71% of the program completed and slightly above the mean number for percentage of completed sessions found in previous online behavioral interventions.⁵⁸

Secondary Analyses, Aim 3b.

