Phase Two: All potential participants will be screened by phone. Potential participants will be identified via self-referral, information is provided by clinical providers or VA staff. Veterans may be provided information on the study by providers and those Veterans tell providers they would like to be contacted by study staff. In addition, Veterans may be identified via a medical record search of potential candidates with a non-cancer chronic pain disorder that come to the clinics listed above. If potential research participants call us about their interest in participating in the study, we will use the attached screening tool and script to assess their eligibility for the study. Patients who are initially screened via

prescreening through the VA Medical Records System, CPRS will be sent a letter regarding their interest, and then called after two weeks if they do not opt out. We will call Veterans to determine their interest in the study, and conduct a screening with the attached screening tool and script. For participants that have indicated to their providers that they would like to be called about the study, and providers have passed on this information to research staff, then research staff will contact them for an initial prescreen for the study (see attached phone script and screen).

Potential subjects will initially be pre-screened by phone to determine whether basic eligibility criteria are met for the study (e.g., age, diagnosis, computer Internet access). Phone pre-screens will be scripted and completed by trained interviewers. Individuals who remain eligible to participate after completion of the phone pre-screen will be invited to participate in usability testing.

Phase 3: We will utilize the same screening procedures as Phase 2 (phone screen for Phase 3 will be different. See attached document).

4.5.1a HIPAA Authorization for Recruitment and/or Screening:

Phase One: We will only ask potential participants if they currently work at the Bedford VAMC, and if they treat Veteran patients for chronic pain concerns. Participants will not be asked for any information regarding their person health or health care.

Phase Two and Phase Three: A request to use identifiable information in the conduct of this research study under a waiver of authorization for recruitment and screening was submitted with this protocol. The identifiable information being requested is:

To use during the recruitment process:

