4.5.2 Enrollment

Phase One: 10-12 subjects will be enrolled in the study by study research staff. A subject will be considered enrolled in the study after the informed consent process.

Confidential and private spaces at the Bedford VA will be used for informed consent process, and for the single in person study visit. Interviews and questionnaires done in person in the VA will be completed with the door closed. A white-noise machine will be used whenever possible to further decrease the risk of participant information being overheard outside of the assessment room.

Phase Two: A maximum of 15 subjects will be consented in the study for usability testing. We assume that for every 3 people we consent, 2 will meet eligibility criteria and participate. For participants eligible for the usability testing session, a subject will be enrolled in the study after the informed consent process if they meet eligibility criteria.

Phase Three: A maximum of 60 subjects will be consented in the study. We assume that for every 3 people we consent, 2 will meet eligibility criteria and become enrolled in the study. For participants eligible for the usability testing session, a subject will be enrolled in the study after the informed consent process if they meet eligibility criteria.

4.5.2a HIPAA Authorization

Phase One: Not applicable. We are not asking providers about their health or healthcare, therefore HIPAA does not apply to this study.

Phase Two: We are requesting a HIPAA waiver from the IRB, as it may be impracticable to obtain a signed HIPAA document from subjects as all research activities will occur remotely. If they do not send back a written HIPAA document we would not be able to use their data.

Phase Three: We are requesting a HIPAA waiver from the IRB, as it may be impracticable to obtain a signed HIPAA document from subjects as all research activities will occur remotely. If they do not send back a written HIPAA document we would not be able to use their data.

4.5.2b Informed Consent:

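### The Phase 3 criteria do not exclude Veterans who already used VACT-CP in Phase 2 usability testing, and no analysis identifies them

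*Combined protocol and SAP*

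**What the plan says.** **Eligibility (Section 4.4, Phase Three).** The seven exclusions cover psychotic disorder, substance use disorder, other pain treatment, cognitive impairment, suicidality, need for a higher level of care, and impairment that prevents computer use. The third reads "Current use of any other chronic pain-related behavioral or psychological treatment". A past VACT-CP session is neither current nor another treatment, so it does not trigger this criterion.

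**Phase 2 exposure (Sections 3.4 and 4.5.2).** The cap is stated as "A maximum of 15 subjects will be consented in the study for usability testing". Staff will "ask Veterans to interact with Coach Anne through one of the VACT-CP modules", but "the Veteran will only be provided a portion of the VACT-CP program during this time". Testers complete the System Usability Scale and the adapted usability items. In the interview, "we will also inquire as to whether they would be interested in using the VACT-CP treatment at home beyond this session".

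**Route into Phase 3 (Sections 4.5 and 4.5.1).** Phases 2 and 3 share one recruitment list at one site. For Phase 3 the protocol says "We will utilize the same screening procedures as Phase 2", adding that the Phase 3 phone screen is a different, attached document. The contact log (Sections 4.5.1a and 4.6.1) prevents repeat contact only with Veterans who are ineligible or not interested.

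**Phase 3 use of the data (Sections 3.4 and 3.5).** On the primary Phase 3 analysis the plan says "We will focus on usability of the VACT-CP system in home setting to test Aim 3a". It correlates usability perceptions with intention and with modules completed, and reports the proportion finishing at least 5 modules. Table 2 marks the usability survey, SUS, working alliance and satisfaction for the intervention group only. Nothing in Section 3.5 records or adjusts for earlier use of the program.

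**The concern.** Phase 3 is meant to show how Veterans receive VACT-CP at home, in preparation for a larger trial whose participants will be new to it. A former tester is not new. That person has met the virtual coach, worked through part of the program and rated it on instruments that Phase 3 uses again. The Analysis Plan describes usability ratings before and after the intervention, while Table 2 shows week 7 only. On either schedule a former tester's rating is not that of a new user.

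Aim 3a and the completion proportion rest on at most 20 people, so two or three such participants carry weight. Aim 3c uses recruitment and retention to decide whether to add a site and to plan the later sample size. Participants who have already joined once may be easier to recruit and retain than new ones. Because nothing identifies former testers, a reader of the results could not tell whether any of this had happened.

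**Working it through.** **The plan's own figures.** Section 4.5.2 expects two of every three consented Veterans to be eligible: 60 × 2/3 = 40, which matches the randomization target. The power paragraph's 125 also reproduces. With a medium effect taken as d = 0.5 (an assumption), 4 × (1.960 + 0.842)² / 0.5² = 125.6. This point depends on neither the power figure nor any change to it.

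**Inputs.** Phase 2 Veterans: planned 12–15, maximum 15. Randomized: 40, allocated 1:1, 20 per arm (Sections 3.2 and 3.3). Attrition after randomization: 30% (Section 3.3). Source pool: 2,605 Veterans (Section 4.1).

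**How many could repeat.**
- Floor: zero.
- If Phase 3 were a random draw of 40 from the pool: expected repeaters 40 × 12/2,605 = 0.18 to 40 × 15/2,605 = 0.23, with a 17–21% chance of at least one. Self-selection would raise this.
- If all 15 volunteer and two in three are eligible: 15 × 2/3 = 10, and 10/40 = 25%.
- Ceiling: 15/40 = 37.5%.

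**Effect on results.** Let e be the number exposed in an arm of 20.
- Shift in the VACT-CP arm's usability mean = (e/20) × difference between exposed and new users, assumed 0.2–0.8 SD.
- Shift in the completion proportion = (e/20) × difference in completion, assumed 10–30 percentage points.
- Dilution of the wait-list contrast = (e/20) × 0.5 SD × fraction of the effect already held, assumed from 1/7 (one module of seven) to all of it.

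| Repeaters | Share of 40 | e per arm (average) | Usability mean (SD) | Completion (points) | Dilution (SD) |
|---|---|---|---|---|---|
| 2 | 5% | 1 | 0.01–0.04 | 0.5–1.5 | 0.004–0.025 |
| 4 | 10% | 2 | 0.02–0.08 | 1–3 | 0.007–0.05 |
| 10 | 25% | 5 | 0.05–0.20 | 2.5–7.5 | 0.018–0.125 |
| 15 | 37.5% | 7.5 | 0.075–0.30 | 3.8–11.2 | 0.03–0.19 |

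The split between arms is left to chance. With 4 repeaters, the probability that all fall in one arm is 2 × C(20,4)/C(40,4) = 10.6%. With 15, the 95% range in one arm is 5 to 10.

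**Effect on a correlation (Aim 3a).** At 30% attrition, 20 × 0.7 = 14 remain in the VACT-CP arm. Suppose 3 of the 14 are former testers who sit 0.8 SD higher on both usability and use, and the true correlation is zero. The mixture adds p(1 − p) × 0.8² = (3/14)(11/14)(0.64) = 0.108 to the covariance and to each variance. The correlation becomes 0.108/1.108 ≈ 0.10. This is an illustration; the documents give none of these differences.

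**Effect on recruitment (Aim 3c).** 60 recruits over 15 months is 4 per month. At the ceiling, 15 of the 60 (25%) would be former testers, and recruitment of new Veterans would be 45/15 = 3 per month.

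**The case against.** Several counter-arguments have force.

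- *The phone screen is unseen.* It is a separate attachment and may already ask about Phase 2. This stands, so the claim is limited to Section 4.4 and the Analysis Plan. If the question is asked there, the governing criteria should still say so.
- *Exposure is small.* It is one session of about two hours with part of the program: roughly 10 minutes of walk-through and 30 minutes of contextual interview. By week 7 a new user who kept going will also know the interface. This stands and argues for the lower ends of the ranges.
- *Higher levels do not by themselves bias a correlation, and a returning user could lose interest.* Correct. Distortion arises when former testers differ on both variables, and its direction is not certain.
- *Cost and harm use different denominators.* If 15 testers really would enrol, replacing them at 3–4 recruits per month takes about 4–5 months (15/4 = 3.8; 15/3 = 5). With one or two repeaters, both harm and cost are small. This is fair.
- *The criteria are deliberately wide (Section 4.5.1b), and recording exposure would be enough.* Recording with a sensitivity summary is a workable fallback, but with 20 users or fewer it repairs less than keeping the samples separate.

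A reader might infer that exposed Veterans in both arms bias both the usability and the wait-list results. The documents do not support that. Table 2 confines the usability, alliance and satisfaction measures to the intervention group. Randomization balances former testers in expectation, so the wait-list contrast is diluted or unbalanced by chance, not pushed one way. Aim 3b reports only means and standard deviations. A reader might also infer that the home-use question builds a list of favourable volunteers, or that testers see their own suggestions adopted. The plan says neither: it only asks the question, and only near-unanimous themes must be acted on.

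**Conclusion.** The gap holds on the page. Section 4.4 admits former Phase 2 testers, the shared recruitment and screening route does not visibly stop them, and no analysis would identify them. The exposed results are the intervention-arm ones: Aim 3a usability and use, and the proportion completing at least 5 modules. Aim 3c recruitment and retention could also be affected. The wait-list effect is slight dilution.

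The size is unknown because the number of repeaters is unknown. The 37.5% ceiling needs every tester to volunteer and qualify, so it is a bound and not an estimate; 25% still needs every tester to volunteer. With one or two former testers in the VACT-CP arm, the usability mean moves by at most 0.08 SD and the completion proportion by at most 3 points under the assumed differences. This is a design gap that should be closed because closing it is easy. It is not a demonstrated bias, and it would not invalidate the pilot.

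**What to change.** Add to the Phase Three exclusions in Section 4.4: *Participation in Phase 2 usability testing of VACT-CP, or any other prior use of the VACT-CP program.* Check it at the phone pre-screen against the master list (Section 4.5.2c), which already records every consented participant, and align the Phase 3 phone screen with it.

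If any former tester has already been randomized, keep that person in the main analysis, as the intent-to-treat statement in Section 3.5 requires. Report prior exposure by arm, and add a sensitivity summary of Aims 3a and 3c without those participants.

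Cost: one line, one look-up, and at most 15 fewer candidates from about 2,605 (15/2,605 = 0.6%). No sample-size figure changes. If many testers would have enrolled, recruitment takes correspondingly longer, up to the 4–5 months shown above.
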